10.0 Procedures Involved

10.1 Provide a description of **all research procedures or activities** being performed and when they are performed once a subject is screened and determined to be eligible. Provide as much detail as possible.

NOTE: This should serve as a blueprint for your study and include enough detail so that another investigator could pick up your protocol and replicate the research. For studies that have multiple or complex visits or procedures, consider the addition of a schedule of events table in in your response.

Response:

Screening Visit: Consent will be explained and signed. Fasting labs before 10:00am include; CBC, CMP, HbA1c, lipid panel, C-peptide and GAD-6 and a urine pregnancy test. Physician preformed physical and medical history, including; blood pressure, height and weight. Blood samples of patients with negative GAD-65 antibodies will be screened for islet cell antibodies, if patient had evidence of auto- immunity to beta cells in the past, they will be retested during screening. Patients with no evidence of autoimmunity to beta cells will not be included in this trial.

Study Visit day -14: After screening visit, qualifying patients will see a registered dietitian who will review their carbohydrate counting and diet and make an assessment of their calorie and carbohydrate intake. Then they will be seen by a CDE for instructions on

injection technique and CGM insertion. The patients will be blinded to CGM. Patients who have been using CGM prior to enrolling in the study can continue to use their CGM's (unblinded). All subjects will be advised to monitor their capillary blood glucose by fingerstick before and 2 hours after each meal and to wear their CGM constantly for a week. The subjects will also be asked to keep a diary of their food intake for a week to measure their calorie intake. Study subjects will not change the type of glucose meter during the trial. They will have their body composition measured by DEXA and MRI prior to the next visit. Smoking patients will be asked not to change their smoking habits during the study.

Study visit day -7: Meal challenge test: In order to assess the changes induced by liraglutide, a meal challenge will be carried out prior to and following liraglutide (week 0 and week 26): a 910 calorie high fat high carbohydrate meal will be given, as in several of our previous papers(20).Bolus dose will be given at 3-4 hours after the ingestion of the meal based on the blood sugar and correction factor for each individual subject as giving bolus insulin immediately before meal may confound the true effects of liraglutide. Acetaminophen (1000 mg for body weight <125lbs, 1250 mg for body weight 125-150 lbs, 1500 mg for body weight 151-175 lbs and 1750 mg for body weight >175 lbs) will be ingested at the beginning of the meal, and the blood levels of acetaminophen will be determined at intervals for assessment of the rate of gastric emptying. Liraglutide will be injected only at week 26 (45 min prior to the meal). Sequential blood samples will be obtained at 0, 15, 30, 45, 60, 90, 120, 150, 180, 210, 240 and 300 min. Samples at 15, 30, 45, 90, 150 and 210 min will be 5 ml while those at 0, 60, 120, 180, 240 and 300 min will be 30 ml (total volume=210 ml). Blood will be collected from an indwelling intravenous canula in a superficial forearm vein.

Study visit day -1: Subjects will come fasting for this visit. Records of blood glucose concentrations monitored by fingerstick and CGM for the previous 14 days will be obtained to assess their glycemic control prior to liraglutide treatment (**this will serve as the baseline assessment of mean blood glucose for the study**). The subjects will have their 24 hour blood pressure measurements completed. Brachial reactivity will be assessed by measuring by flow mediated dilation (FMD). They will undergo a meal challenge test (described below) and a fat biopsy. 24 hr urine will be collected.

Study Visit day 0: Subjects will come fasting for this visit. Each subject will be given one injection of Liraglutide 1.2 mg or placebo. A fructosamine and blood samples will be collected at baseline. Blood samples will be collected after the baseline at 30, 60, 120, 180, 240 and 300 minutes after the injection. (**This is being done to evaluate the acute effect of a single injection of Liraglutide on oxidative stress and inflammatory mediators, before any adjustments of insulin dose or effect of Liraglutide on blood glucose and weight is evident**). Subjects will be instructed by the study staff in the dosing and administration of the study medication. They will start Liraglutide injection at a dose of 0.6 mg per day or placebo injection on the following day. We will adjust the doses of basal and bolus insulin to eliminate low blood sugars(less than 70 mg/dl). At all subsequent visits insulin doses will be titrated to target blood sugars between 70-180 mg/dl at all times. Patients will return to the center after 7 days.

Study Visit week 1: Blood glucose concentrations will be reviewed. Insulin dose will be adjusted at the discretion of the study investigator to optimize blood sugar control as per

the targets mentioned above. Patients will be advised to increase the Liraglutide dose to 1.2 mg a day if they are able to tolerate the 0.6 mg dose. If they are experiencing mild nausea, subjects will continue with 0.6 mg daily for another 7 days. Those with severe nausea/vomiting will be dropped from the study. All other subjects will return in 7 days.

Study Visit week 2: Blood glucose concentrations will be reviewed. Insulin dose will be adjusted if needed. Subjects taking 0.6 mg dose and experiencing significant nausea will be dropped from the study. Subjects on 1.2 mg and experiencing significant nausea will decrease the dose to 0.6 mg and continue that dose for the duration of the study. Subjects on 1.2mg and experiencing mild nausea will continue on 1.2 mg for 2 more weeks. Subjects on Liraglutide 1.2mg daily without any gastro-intestinal side-effects will be asked to increase the dose to 1.8 mg daily. Study drug will be dispensed for additional 2 weeks.

Study Visit week 4: Subjects will be asked to bring in their used study pens and the pen that they are using so that study nurse can log in the amount of drug used. If needed, the dose will be increased. The goal in the first 4 weeks is to increase patient's liraglutide dose to maximum tolerated dose. Maximum dose of liraglutide will be 1.8 mg daily. Subjects experiencing mild nausea with 0.6 mg or 1.2 mg will continue at that dose in the study. Those with severe nausea/vomiting with 1.8mg will decrease their dose to 1.2 mg and continue that dose throughout the study. Blood glucose concentrations will be reviewed. Insulin dose will be adjusted if needed. CGM will be discontinued. Study drug will be dispensed to last till the next visit.

Study visit week 8: Subjects will be asked to bring in their used study pens and the pen that they are using so that study nurse can log in the amount of drug used. Blood glucose concentrations will be reviewed. Insulin dose will be adjusted if needed. Study drug will be dispensed to last till the next visit.

Study Visit week 12: Subjects will be asked to bring in their used study pens and the pen that they are using so that study nurse can log in the amount of drug used. Blood glucose concentrations will be reviewed and vascular activity will be performed. Insulin dose will be adjusted if needed. Fasting blood, research labs, HbA1c, fructosamine, lipid panel, urine pregnancy test and 24 hr urine will be collected. FMD and 24hr blood pressure will be studied. Study drug will be dispensed for additional 4 weeks.

Study Visit week 16 and 20: Subjects will be asked to bring in their used study pens and the pen that they are using so that study nurse can log in the amount of drug used. Blood glucose concentrations will be reviewed. Insulin dose will be adjusted if needed. Study drug will be dispensed for additional 4 weeks.

Study visit week 24: CGM will be inserted. They will have their body composition measured by DEXA and MRI prior to next visit.

Study Visit week 26: Subjects will come fasting for this visit. Research labs, CBC, CMP, Lipids, HbA1c and fructosamine will be collected. Records of blood glucose concentrations monitored by finger-stick and CGM for the previous 14 days will be obtained to assess their glycemic control. They will undergo meal challenge test (described above) and a fat biopsy. 24 hr urine will be collected. FMD and 24hr blood pressure will be performed. After this visit, subjects will be discharged from the study.

Blood samples (collected in protease and DPP-IV inhibitors) will be appropriately processed and assayed for glucose, C-peptide, glucagon, GLP-1 and gastric inhibitory peptide (GIP) which is also called gastric insulinotropic peptide, Reactive oxygen species (ROS) generation, Thiobarbituric acid reducing substances (TBARS), urinary isoprostanate,

intranuclear nuclear factor kappa B (NFkB) binding, the expression and concentration of Toll like receptor-4 (TLR-4), tumor necrosis factor alpha (TNF α), Inhibitor kappa B (IkB α), Matrix metalloproteinase 9 (MMP-9), Suppressor of cytokine signaling-3 (SOCS-3), Protein kinase C (PKC β II), Phosphotyrosine phosphatase -1B (PTP-1B), Glycogen synthase kinase 3 beta (GSK-3 β), Inhibitor kappa kinase (IKK β), C-jun amino terminal kinase (JNK-1) and amount of Insulin receptor (IR- β) and p-IR β in MNC and plasma concentrations of C-reactive protein (CRP), Monocyte chemoattractant protein -1 (MCP-1), Plasminogen activator inhibitor -1 (PAI-1), TNF α and Regulated upon activation Normal T cell Expressed and Secreted (RANTES). Adipose tissue samples will be processed and analyzed for intranuclear NFkB binding, the expression and concentration of TLR-4, TNF α , IkB α , MMP-9, SOCS-3, PKC β II, PTP-1B, GSK-3 β , IKK β , JNK-1 and amount of IR- β and p-IR β .

Clinical and Laboratory Procedures

- 1. Plasma glucose, glucagon, C-peptide, GLP-1, GIP and FFA measurements:** Glucose levels will be measured in plasma by YSI 2300 STAT Plus glucose analyzer (Yellow Springs, Ohio) (CV 2% for both intra and inter-assay). Free fatty acid levels will be measured by a colorimetric assay (Wako, Richmond, VA). CBC and comprehensive metabolic panel will be measured using well established assays by the clinical laboratory. C-peptide will be measured with Ultrasensitive ELISA kit (LOD is 2.5 pg/ml with 3.8% and 5.8% intra and inter-assay CVs) (Mercodia, NC). GLP-1 (8% and 7% CVs), GIP (2-6% and 3-8% CVs) and glucagon (<5% and <10% CVs) will be measured from samples collected in protease and DPP-IV inhibitors by ELISA kits form Millipore.
- 2. Fat aspiration procedure:** Adipocytes will be harvested from the subjects by methods previously described in literature (21; 22). Subcutaneous fat tissue aspiration will be performed on abdomen at a 10 cm distance from umbilicus. The subjects will not have taken aspirin or NSAIDS in the last 72 hours. If that is the case, then the procedure will not be done. The skin will first be prepared with povidone-iodine (Betadine) and alcohol. A sterile drape will be placed around the appropriate area. 3 cc of 1% lidocaine will then be administered subcutaneously. After adequate anesthesia has been achieved, approximately 20-50cc of 0.5% lidocaine will be injected in the adipose tissue. Dose of lidocaine will not exceed 4.5mg/kg body weight. Aspiration of fat tissue will then be performed with a 3-holed canula (Tulip Instrumentation, length: 15cm, diameter: 2.1mm) fixed to a 10mL syringe. More than one attempt at aspiration can be done at the same site during the procedure to get adequate sample. After getting adequate fat tissue (500mg-3g), the puncture site will be pressed for at least ten minutes before the patient rises up from supine position (to minimize bruising). The study subjects will then be discharged home. The adipose tissue will be centrifuged to remove blood and fluid contaminants. The upper adipose tissue will be collected into a separate sterile tube, washed twice with cold sterile Phosphate Buffered Saline (PBS) and centrifuged to remove the PBS. The adipose tissue sample will be weighed and approximately 500 mg transferred to a separate tube for analysis. Total RNA, nuclear extracts and total cell lysates will be prepared from the adipose tissue.
- 3. MRI and DEXA:** Multislice MRI of abdomen will be obtained(23). Abdominal subcutaneous adipose tissue, hepatic fat and intra-abdominal adipose tissue (adipose

tissue in the intra-abdominal cavity delineated at the innermost aspect of the abdominal and oblique muscle walls surrounding the cavity and the anterior aspect of the vertebral body. MRI images will be analyzed in a blinded fashion using customized software (24).MRI measurements will be expressed as volume in cm^3 . All measurements will be done at one center, by the same machine and using the same software. The coefficient of variation of MRI measured abdominal subcutaneous fat is 1-2% and of visceral fat is 3-6%(25; 26). DEXA will be used to measure lean body mass. Adipose tissue mass will be calculated by subtracting lean body mass from total body mass. Adipose tissue mass will be expressed as kilograms. All measurements will be done at one center and by the same machine using the same software. The within-center variability over time in measurement by DEXA of lean mass is 0.9% and of fat mass is 1.2% (27).

4.24 Hr Blood Pressure monitoring: Ambulo 2400 24-hour Ambulatory Blood Pressure Monitoring (ABPM) system from Tiba Medical will be used.

5. **Brachial flow-mediated dilatation (FMD):** FMD is the capacity of blood vessels to respond to an increase in flow, or more precisely shear stress, by dilating. Endothelium-derived nitric oxide is a principal mediator of FMD. A 7.5 – 10 MHz broadband multi-frequency linear array transducer will be used to acquire images. The subject is positioned supine with the arm in a comfortable position for imaging the brachial artery. To create a flow stimulus, a blood pressure cuff is placed on the forearm. After acquiring a baseline rest image, arterial occlusion is created by cuff inflation to suprasystolic pressure. To occlude arterial inflow for a standardized length of time, the cuff is inflated to at least 50 mm Hg above systolic pressure. The resultant ischemia triggers dilatation of downstream resistance vessels via autoregulatory mechanisms. Following 5 minutes of occlusion, the cuff is deflated. This results in reactive hyperemia (a brief high-flow state) in the brachial artery to accommodate the dilated resistance vessels. The shear stress that results causes dilatation of the brachial artery. The recording of the arterial image is done continuously from 30 seconds before to 2 minutes following cuff deflation(28). This procedure has been utilized in several studies carried out in our unit, including the first studies describing abnormalities in African Americans(29), brachial reactivity improvements related to reversal of oxidative stress in the obese and type 2 diabetics following troglitazone(30) and gender differences in brachial reactivity and the effect of hormone replacement therapy (HRT) in post-menopausal women(31).
6. **Questionnaires:** The 36-item short form health survey version 2(SF-36, RAND corporation, Santa Monica, CA) will be used to measure quality of life. Depression will be assessed by the Patient Health Questionnaire (PHQ) Depression Measure (Pfizer Inc, New York, NY).(32; 33)
7. **MNC isolation:** Blood samples will be collected in Na-EDTA as an anticoagulant. Three and a half mL of anticoagulated blood sample are carefully layered over 3.5 mL of PMN medium (Cedrlane Laboratories, Hornby, ON). Samples are centrifuged and at the end of the centrifugation, two bands separate out at the top of the RBC pellet. The top band consists of MNC, while the bottom consists of PMN. The MNC band is harvested and washed twice with Hank's balanced salt solution (HBSS). This method provides yields greater than 95% pure PMN and MNC suspensions.

8. NFκB DNA binding activity: Nuclear NFκB DNA binding activity is measured by EMSA. Nuclear extract is prepared from MNC and adipose tissue by high salt extraction as described by Andrews et al (34). The specificity of the bands is confirmed by supershifting these bands with specific antibodies against Rel-A (p65) and p50 (Santa Cruz Biotechnology, CA) and by competition with cold oligonucleotides. DNA binding activity of NFκB will be adjusted to Oct-1 DNA binding activity to correct for any variable.

9. Plasma concentrations of inflammatory mediators: Concentrations of TNF α (CV: 5.3% Intra and 8.1% inter-assay, LD: 0.1pg/ml), MMP-9 (CV: 2.2% Intra and 7.1% inter-assay, LD: 0.156ng/ml), MCP-1 (CV: 5.7% Intra and 5.2% inter-assay, LD: 1.7pg/ml) and RANTES (CV: 3.2% Intra and 8.8% inter-assay, LD: 2.0pg/ml) are measured in plasma using ELISA kits (R&D Systems, MN). CRP concentrations (CV: 3.5% Intra and 5% inter-assay, LD: 0.35ng/ml) will be measured using an ELISA kit from Alpha Diagnostics International Inc. (San Antonio, TX)

10. ROS generation measurement by chemiluminescence: Five hundred μ L of MNC (2×10^5 cells) are delivered into a Chronolog LumiAggregometer cuvette. Luminol is then added, followed by 1.0 μ L of 10 mM formylmethionyl leucinyl phenylalanine (fMLP). Our method (**CV intra= <6% and intra= <9%**), developed independently is similar to that published by Tosi and Hamedani (35).

11. 15-isoprostane F_{2t} (also known as 8-epi-PGF α or 8-iso-PGF α) in urine samples will be measured by an ELISA kit from Oxford Biomedical Research (Oxford, MI).

12. 7%\$56 will be measured using the a commercial kit (CVs, intra=6.4% and inter= 8.6%) from Zeptometrix (Buffalo, NY)

13. Quantification of TLR-4, I κ B α , TNF α , MMP-9, SOCS-3, PKC- β II, IR- β , PTP-1B, GSK-3 β IKK β and JNK-1 mRNA, IR β and pIR β in MNC by Real-Time Reverse Transcription Polymerase Chain Reaction (RT-PCR): Total RNA is isolated from MNC and adipose tissue using commercially available RNAqueous®-4PCR Kit (Ambion, Austin, TX) The quality and quantity of the isolated RNA is determined before using the RNA. Real Time RT-PCR is performed using Cepheid Smart Cycler (Sunnyvale, CA) in which 2 μ L cDNA, 10 μ L Sybergreen Master mix (Qiagen, CA) along with 0.5 μ L of 20 μ M gene specific primers ([name]) are used. The specificity and the size of the PCR products are tested by adding a melt curve at the end of the amplifications and by running it on a 2% agarose gel. All values are normalized to 18S expression.

14. Western blotting of TLR-4, I κ B α , IKK β , IR- β , p-IR- β , JNK-1, SOCS-3, PKC- β II, GSK-3 β and PTP-1B: MNC and adipose tissue total cell lysates will be prepared lysis buffer. Sixty μ g of total cell lysate are boiled in SDS buffer and proteins separated by SDS-PAGE and then transferred to PVDF membrane. Polyclonal or monoclonal antibodies against, TLR-4, I κ B α , IKK β , IR- β , p-IR- β , JNK-1, SOCS-3, PKC- β II, GSK-3 β and PTP-1B are used and the membranes are developed using super signal, chemiluminescence reagent (Pierce Chemical, IL). Densitometry is performed using molecular analyst software (Biorad, CA) and all values are corrected for loading with actin.

10.2 Describe what data will be collected.

NOTE: For studies with multiple data collection points or long-term follow up, consider the addition of a schedule or table in your response.

Response: The following data will be collected during the conduct of the study based on the study design and protocol: HbA1c, fructosamine, average glucose, percent time spent in different glycemic thresholds, standard deviations which represent the variability in blood glucose, total insulin doses (basal dose, bolus dose and total daily dose), changes in carbohydrate intake and helpings; adverse events(including the most common side effects of nausea and vomiting which is often transient occurring at the time of initiation of liraglutide and at the time of escalation of the dose and the rare occurrence of pancreatitis, thyroid c-cell tumors and other patient reported adverse events which may occur anytime) and blood pressure. The principal investigator [name], PhD and co-investigators [name] and [name] will review the data every 3 months to assess the safety of the participants. Furthermore they will also assess other risks including the physical, psychological, social, legal and economic harm to these patients. The investigators listed above will carefully watch for any invasion of privacy and breach of confidentiality. The principal investigator will be sharing the results of safety analysis of the study with the sponsor (JDRF) and to the IRB. The study groups will remain blinded. If there are any safety concerns then co-investigator [name] who is not directly involved with the patients and or in insulin titrations of the study participants will unblind the study groups on the discretion of principal investigator and the team will assess potential harm to the patients and inform the IRB and sponsor of this potential harm. The corrective actions will then be taken and research subjects will be withdrawn from the study if risks outweigh the benefits. The IRB will be kept well-informed at all times. During each patient visit, evolution of glucose levels (CGM) will be conducted to reduce the risk of hypoglycemia or hyperglycemia. After recruitment and completion of half of the target number of patients i.e. 42 patients, interim analysis will be performed to determine an overwhelming harms or benefits with one treatment option compared to another.

 10.3 List any instruments or measurement tools used to collect data (e.g. questionnaire, interview guide, validated instrument, data collection form).

Include copies of these documents with your submission.

Response: Source documents will be used to collect patient information. Patients CGM, dietary intake, BP, weight are monitored every visit to ensure safety. CGM graphs will be evaluated every visit.

10.4 Describe any source records that will be used to collect data about subjects (e.g. school records, electronic medical records).

Response: electronic medical records and research files.

10.5 Indicate whether or not **individual** subject results, such as results of investigational diagnostic tests, genetic tests, or incidental findings will be

shared with subjects or others (e.g., the subject's primary care physician) and if so, describe how these will be shared.

Response: Individual participant lab results will be disclosed to the participant upon their request. If the participant requests documentation be shared with another physician, physician office or hospital the participant must come to the research center to collect said documentation or the documentation can be mailed to their given home address.

10.6 Indicate whether or not **study** results will be shared with subjects or others, and if so, describe how these will be shared.

Response: Not Applicable. Study results will not be shared with the subjects. However, unidentifiable study results could be published in the form of a manuscript or abstract and will be reported to JDRF and to clinicaltrials.gov.

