4.0 Study Design

4.1 Describe and explain the study design (e.g. case-control, cross-sectional, ethnographic, experimental, interventional, longitudinal, observational).

Response: This investigation will be a prospective, randomized, double blind, placebo controlled parallel design study conducted in patients with type 1 diabetes. The study will be conducted at Diabetes-Endocrinology Center of WNY, affiliated to the State University of New York at Buffalo.

84 overweight or obese patients with type 1 diabetes on treatment with either continuous subcutaneous insulin infusion (CSII; also known as insulin pump) or multiple (four or more) injections of insulin per day will be included in the study. They will be randomized into 2 groups of 42 patients each. The patients will be randomized to daily subcutaneous injections of placebo or liraglutide. In view of the possibility of hypoglycemia and the side effect of nausea all patients will be started on 0.6 mg of liraglutide per day. The dose will then be titrated up to 1.8 mg.

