6.0 Inclusion and Exclusion Criteria

6.1 Describe the criteria that define who will be **included** in your final study sample.

NOTE: This may be done in bullet point fashion.

Response:

- 1) Type 1 Diabetes on continuous subcutaneous insulin infusion (CSII; also known as insulin pump) or multiple (four or more) injections of insulin per day.
- 2) Using a continuous glucose monitoring device (CGM) or regularly measuring their blood sugars four times daily.
- 3) HbA1c of less than 10.0%.
- 4) Well versed with carbohydrate counting.
- 5) Age 18-80 years
- 6) $BMI \geq 25 \text{ kg/m}^2$
- 7) Age at diagnosis of type 1 diabetes should be <30 years.
- 8) Evidence of auto-immunity to beta cells (GAD-65 and islet cell antibody screen)

6.2 Describe the criteria that define who will be **excluded** from your final study sample.

NOTE: This may be done in bullet point fashion.

Response: 1) Type 1 diabetes for less than 6 months;
2) Coronary event or procedure (myocardial infarction, unstable angina, coronary artery bypass, surgery or coronary angioplasty) in the previous four weeks;
3) Hepatic disease (transaminase > 3 times normal) or cirrhosis;
4) Renal impairment (serum eGFR $<30 \text{ ml/min/1.73m}^2$);
5) HIV or Hepatitis B or C positive status;
6) Participation in any other concurrent clinical trial;
7) Any other life-threatening, non-cardiac disease;
8) Use of an investigational agent or therapeutic regimen within 30 days of study.
9) history of pancreatitis
10) pregnancy
11) inability to give informed consent
12) history of gastroparesis

- 13) history of medullary thyroid carcinoma or MEN 2 syndrome.
- 15) Use of any agent other than insulin for treatment of diabetes (metformin, pramlintide or thiazolidinediones;
- 16) painful gallstones;
- 17) alcoholism;
- 18) hypertriglyceridemia (>500 mg/dl)
- 19) History of pancreatitis

6.3 Indicate specifically whether you will include any of the following special populations in your study using the checkboxes below.

NOTE: Members of special populations may not be targeted for enrollment in your study unless you indicate this in your inclusion criteria.

Response: None of the below populations will be enrolled

- Adults unable to consent
- Individuals who are not yet adults (infants, children, teenagers)
- Pregnant women
- Prisoners

6.4 Indicate whether you will include non-English speaking individuals in your study. **Provide justification if you will exclude non-English speaking individuals.**

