17.0 Data Management and Analysis

17.1 Describe the data analysis plan, including any statistical procedures. This section applies to both quantitative and qualitative analysis.

Response: The focus of the proposed research is to evaluate the effect of liraglutide on mean HbA1c% over the period of 26 weeks of treatment. The similarities between the study groups, baseline values for subject's demographics and study endpoints will be compared using appropriate parametric tests. Transformations of the data in order to meet statistical assumptions may be considered. The **primary endpoint** of the study is to detect

a difference in HbA1c after 26 weeks of treatment with Liraglutide or placebo. The statistical analysis will be carried out using analysis of covariance (ANCOVA) and tested at the 0.05 level. Change in weight will be a covariate. The results will be computed as mean \pm SD. Analysis will be carried out on the basis of intention to treat (with last observation carried forward).

The secondary end points based on glycemic changes will include the difference from baseline in mean weekly glucose concentrations, standard deviations of the mean weekly glucose concentrations, HbA1c, fructosamine, the duration of time spent in hyperglycemia ($>150\text{mg/dl}$, $>200\text{mg/dl}$, $>250\text{mg/dl}$) and hypoglycemia ($<70\text{mg/dl}$, $<40\text{mg/dl}$), insulin dosage. A reduction in the AUC following the meal will constitute another secondary end point. Between groups comparisons of the magnitude of change from baseline will also be made for these glycemia related secondary endpoints using student's t-test. Comparisons for these and the primary endpoints will also be made using the paired t-test or Wilcoxon's test for paired data within each group.

The other secondary end-points of the study will be change from baseline after 26 weeks of treatment in the fasting and postprandial blood sugars, glucagon and C-peptide concentrations, indices of oxidative and inflammatory stress in MNC, plasma and adipose tissue; subcutaneous fat mass, hepatic fat content and visceral fat mass; features of metabolic syndrome; gastric emptying, blood pressure, vascular analysis, patient reported nausea, quality of life and depression scores. Between groups comparisons will be made using students t-test or ANCOVA (adjustment will be done for baseline differences). Within group comparisons for these endpoints will be made using paired t-test or Wilcoxon's test or ANCOVA.

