17.2 If applicable, provide a power analysis.

NOTE: This may not apply to certain types of studies, including chart/records reviews, survey studies, or observational studies. This question is asked to elicit whether the investigator has an adequate sample size to achieve the study objectives and justify a conclusion.

Response: There are no prior randomized controlled trials that have examined the effect of Liraglutide on HbA1c in subjects with type 1 diabetes. In our observational study (preliminary data), we found a decrease in HbA1c of 0.35% after 6 months of liraglutide in patients with type 1 diabetes who had a mean HbA1c of $6.45\pm0.5\%$. In our proposed study, we will include patients with HbA1c up to 8.5%. Thus we expect a greater difference in HbA1c among the two groups at the end of the study. Conservatively estimating a difference in HbA1c of 0.35% between the two groups, a sample size of 32 patients per treatment group should provide 80% power to detect a significant difference ($\alpha = 0.05$), provided the standard deviation of the residuals is not greater than 0.5. Thus 64 subjects will be needed for the study. To account for a dropout rate of 30%, we will recruit 84 subjects into the study.

17.3 Describe any procedures that will be used for quality control of collected data.

Response: Three investigators and research nurse will double check the accuracy of collected data. All laboratory testing will be standardized using references and standards.

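### CGM mode (own unblinded or study blinded) and insulin delivery (pump or injections) vary at entry but are neither strata nor covariates; adjusting for both would give a small, nearly free gain in precision and credibility

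*Combined protocol and SAP*

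**What the plan says.** Section 6.1 admits patients on an insulin pump or on four or more injections a day. For glucose monitoring it accepts patients "Using a continuous glucose monitoring device (CGM) or regularly measuring their blood sugars four times daily".

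Section 10.1 (day -14) fits a CGM whose readings the patient cannot see, then makes an exception: "Patients who have been using CGM prior to enrolling in the study can continue to use their" own devices unblinded. At week 4 it stops CGM and at week 24 it inserts it again, without saying whether the week 4 stop covers personal devices.

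On allocation, section 4.1 says "The patients will be randomized to daily subcutaneous injections of placebo or liraglutide", with 42 per group. Section 11.2 repeats 42 and 42. No blocks, strata or minimisation are described in either place.

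On analysis, section 17.1 says: "The statistical analysis will be carried out using analysis of covariance (ANCOVA) and tested at the 0.05 level". It then names one covariate: "Change in weight will be a covariate". Adjustment for baseline differences is mentioned only for the non-glycaemic group of secondary endpoints, and neither CGM mode nor insulin delivery is named there. The glycaemic secondary endpoints, including weekly mean glucose, its SD and time in low and high ranges, are compared between arms by t-test.

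**The concern.** A patient who sees a continuous display can act on it between visits. A patient on a blinded sensor or on fingersticks cannot do so to the same degree. Pump and injection users may also respond differently when insulin is retitrated. Either factor could therefore relate to HbA1c change, insulin dose, hypoglycaemia and the CGM endpoints. Both are established when eligibility is judged, so handling them needs no new data.

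The pilot behind the planned difference was more uniform: section 3.1 describes its patients as being on pump and CGM. The trial widens that background but leaves it out of the model. With 42 per arm, a visible imbalance in either factor is quite possible. A reader could then ask whether the HbA1c result reflects liraglutide or background monitoring, and an adjustment chosen after seeing the data would be open to dispute.

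**Working it through.** **Inputs from the documents (17.2).** "Conservatively estimating a difference in HbA1c of 0.35% between the two groups"; "provided the standard deviation of the residuals is not greater than 0.5"; "a sample size of 32 patients per treatment group should provide 80% power to detect a significant difference". Alpha is 0.05, taken as two-sided because the side is not stated. There are 42 per arm (4.1).

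**Inputs not in the documents (assumptions).** Share *p* of patients with their own unblinded CGM: 20% to 50%. Effect *b* of that factor on HbA1c change over the trial: 0.2 to 0.5 points. The same formulas apply to pump versus injections, for which the documents also give no figures.

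**1. The plan's own figure.** n per arm = 2 × (1.960 + 0.842)² × 0.5² / 0.35² = 32.04. The stated 32 gives power 0.7996 by the normal formula (0.787 by the t distribution), so the plan's figure is reproduced.

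**2. Standard error of the HbA1c difference.** 0.5 × √(2/42) = 0.109 with all 84 patients; 0.5 × √(2/32) = 0.125 with 32 per arm.

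**3. Size of a chance imbalance.** With unstratified 1:1 allocation, the SD of the between-arm difference in proportions is √(2p(1-p)/42). At p = 0.5 this is 0.109, or 11 percentage points (its match with the HbA1c standard error is a coincidence). At p = 0.3 it is 10 points and at p = 0.2 about 9 points.

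**4. Shift in the arm difference** (imbalance × *b*), at p = 0.5:

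| Imbalance | Chance of this or larger | Shift, b = 0.2 to 0.5 | Shift / 0.109 |
|---|---|---|---|
| 11 points (1 SD, typical) | not applicable | 0.02 to 0.05 | 0.2 to 0.5 |
| 6 patients = 14 points | 23% to 28% | 0.03 to 0.07 | 0.3 to 0.7 |
| 9 patients = 21 points | about 5-6% | 0.04 to 0.11 | 0.4 to 1.0 |

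The two ends of each chance come from different models: two independent binomials (23.0% and 6.3%), or exactly 42 users split at random between the arms (27.5% and 4.9%; in that case gaps can only be even, so 9 or more means 10 or more). At p = 0.3 a 1-SD imbalance again shifts the difference by 0.02 to 0.05; at p = 0.2, by 0.02 to 0.04.

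**5. What adjustment buys.** Take 0.5 as the SD before adjustment for the factor. One binary term reduces it to √(0.25 - b²p(1-p)). For b = 0.3 and p = 0.5 this is √(0.25 - 0.0225) = 0.477, and power at 32 per arm is Φ(0.35/(0.477 × 0.25) - 1.96) = 0.835. Over p = 20% to 50%, power rises from 80.0% to 81.0-83.5% for b = 0.2 to 0.3, and to 86-90% for b = 0.5. The required sample size is unchanged.

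**The case against.** The strongest reply is that chance imbalance is what the standard error describes. Even the unusual shift of 0.04 to 0.11 is at most about one standard error. It is part of that error, not added to it. This stands, and it rules out calling the design biased.

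Second, the effect of 0.2 to 0.5 points has no support in the documents. The endpoint in 2.1 is change from baseline, and these patients already use their device or delivery method, so an established benefit should already be in baseline HbA1c. Section 3.1 reports no significant change when pilot patients on pump and CGM tried to optimise control over at least two weeks. That observation is short and uncontrolled, but nothing else in the documents bears on the question. This also stands: the effect may be near zero. It is weakened a little because 17.1 speaks of HbA1c after 26 weeks and names no baseline HbA1c covariate. If final values were analysed that way, baseline differences would remain in the comparison.

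Third, a reader might infer that only own-CGM patients can benefit from continuous readings. The documents do not support that. Sections 10.3 and 19.2 have CGM graphs evaluated at visits, section 10.1 has staff review glucose and adjust insulin, and all patients are told to take fingersticks before and after meals. What differs is the patient's real-time view. How long that contrast lasts depends on whether the week 4 stop applies to personal devices, which the text leaves open.

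Fourth, two crossed factors give four cells averaging 21 patients, probably uneven. This stands against stratifying on both.

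**Conclusion.** The omission is real, but its likely consequence is modest. Two baseline factors that may relate to HbA1c change are left in the residual, while the one covariate named is measured after randomisation. Under the stated assumptions, the typical effect on the arm difference is 0.02 to 0.05 HbA1c points against a standard error of 0.109, and adjustment would add about 1 to 3.5 percentage points of power at effects of 0.2 to 0.3. The larger figures need an effect of 0.5, which nothing in the documents supports.

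Three stronger readings should be avoided:

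- The treatment comparison is not biased. Randomisation and the 0.05 test already allow for chance imbalance.
- The 23% chance of a 6-patient gap must not be joined to the shift of 12% to 31% of the planned 0.35. That shift belongs to a 21-point gap, which is about 5-6% likely.
- The trial is not shown to be underpowered on this account. If 0.5 were the SD within a single background type, half the patients were in each group and the effect were 0.2 to 0.5, the SD would be 0.51 to 0.56 and power at 32 per arm 78% to 71%. But 17.2 does not say where 0.5 comes from, and it states the figure as a limit on the residual SD.

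Stratification is undescribed rather than ruled out, since no randomisation method is given at all.

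**What to change.** In 17.1, prespecify two baseline covariates in the primary HbA1c ANCOVA: own unblinded CGM (yes/no) and insulin delivery (pump/injections), both as recorded before randomisation. Use the same terms for the CGM-derived and hypoglycaemia comparisons, which means ANCOVA in place of the planned t-test. Tabulate both factors by arm.

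Stratifying the randomisation in 4.1 is optional. It is worth considering only if randomisation has not begun, and is best limited to one factor because of the small cells.

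The cost is two model degrees of freedom. No extra data or patients are needed, and clinical management does not change.
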